### GROUP 2:

Each subject in Group 2 will participate in the study for up to 26 weeks, including up to approximately 3 weeks for screening, 22 weeks for treatment, and approximately 1 week for follow-up. SC injections of 128 mg CAM2038 q4w will be administered in the buttock, rotating between right and left buttock and injection site per Appendix 17.2, on Day 1, Day 29, Day 57 and Day 85, for a total of 4 doses. Following the first administration, subjects will attend an interim visit on Day 2 to evaluate safety and tolerability of the transition from SL BPN 24 mg to CAM2038 q4w.

Following administration of the first 3 doses, PK samples will be collected pre-dose and at scheduled times post-dose on an outpatient basis to determine achievement of steady state. To

Clinical Study Protocol Braeburn Pharmaceuticals HS-15-549 CONFIDENTIAL characterize steady state PK of BPN and norBPN, subjects will be confined to the CRU and serial PK samples will be collected for up to 24 hours following the fourth dose, administered on Day 85; subsequent PK samples will be collected up to 28 days post-dose on an outpatient basis. At the Day 113 (EOT) visit, CAM2038 q4w 128 mg subjects may continue on with open-label extension phase for up to 6 weeks and will be switched to CAM2038 q1w 32 mg, or transition back to standard care. For those subjects enrolling into the open-label extension, transition back to standard care will begin on Day 155 (EOT - OLE).

At each study visit, safety and efficacy assessments will be conducted at pre-specified times. Subjects will also be required to record their worst daily pain and average daily pain using an 11-point NRS on an electronic device.

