## 9.5 **Prior and Concomitant Therapy**

All non-study medications, including prescription, over-the-counter, or herbal therapies, used by the subject will be documented for the 30 days prior to Screening and throughout Version: 5.0, 05 OCT 2016 Page 35 of 87 Clinical Study Protocol Braeburn Pharmaceuticals HS-15-549 CONFIDENTIAL the study. The Investigator will determine if the prior/concomitant medication(s) affect the subject's eligibility to participate or continue to participate in the study. The following restrictions on concomitant medications will be in place during the study:

- Opioid receptors are likely to be occupied by BPN, which may reduce the analgesic effects of an opioid. The dissociation of BPN from the receptors may take several days following discontinuation of SL BPN treatment, or up to 2 weeks (Group 1) or up to a month (Group 2 [for subjects not entering the open-label extension] and Group 3) following the last CAM2038 injection. Therefore, subjects requiring analgesic emergency treatment or anesthesia for surgery should ideally be treated with a non-opioid analgesic. Opioids may be used with caution, but as higher doses may be required for analgesic effect, there may be a higher potential for toxicity with opioid administration. The clinical course should be carefully evaluated and fully documented for subjects who have a requirement for any opioid analgesic for >7 days continually or general anesthesia for surgery. Particular care should be taken in subjects with chronic respiratory disease, bowel disease and liver disease during anesthesia and the post-operative period.
- BPN is metabolized via CYP3A4. Because CYP3A4 inhibitors may increase plasma concentrations of BPN, if CYP3A4 inhibitors such as azole antifungals (e.g., ketoconazole), macrolide antibiotics (e.g., erythromycin), and HIV protease inhibitors (e.g., ritonavir, indinavir, and saquinavir) are required, the Medical Monitor must be consulted. Interactions with CYP3A4 inducers have not been investigated; therefore it is recommended that the use of agents such as phenobarbital, carbamazepine, phenytoin and rifampicin be avoided in subjects receiving study treatment. The Medical Monitor must be consulted prior to starting subjects on any of these agents.

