### **10.5.1 Adverse Events and Serious Adverse Events**

#### **Adverse Event Reporting** 10.5.1.1

Throughout the study, AEs will be documented on the appropriate page of the CRF whether or not considered treatment-related. This includes any new signs, symptoms, injury or illness, including increased severity of previously existing signs, symptoms, injury, or illness. CAM2038 injections sites will be examined during each scheduled visits for any signs of adverse site reactions, including erythema, pruritus, edema, pain, etc. The new injection site will also be examined shortly minutes after each injection to determine if any site related AEs have occurred. Subjects will also be queried specifically about local tolerability AEs in connection to the examinations.

Conditions existing prior to dosing will be recorded as part of the subject's medical history. The Investigator is responsible for assessing the relationship of AEs to the study drug; relationship will be classified as not related, unlikely related, possibly related, or probably related (see Section 10.5.1.2 for definitions).

All AEs and SAEs will be collected by the Investigator from the time informed consent is signed until 7 days after the EOT visit. This includes any AEs that are ongoing at the completion/termination of the study, and any AEs that start after the last dose of study drug. SAEs and AEs that have been designated as possibly related to study drug will be followed until resolution or stabilization. Any SAEs considered related to study drug should be reported to the Sponsor without regards to these timelines.

Any SAE, including death resulting from any cause, which occurs to any subject participating in this study or within 14 days of the EOT visit or premature discontinuation from the study whether or not related to the study drug, must be reported via email, facsimile or telephone within 24 hours of first being advised of the SAE. Follow-up information collected for any initial report of an SAE must be reported to the Sponsor or designee within 24 hours of receipt by the Investigator. In the event discussion is necessary call the Medical Monitor.

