## **11.4** ADVERSE EVENTS

Each AE and SAE term recorded on the case report forms (CRFs) by primary system organ class (SOC) and will be mapped to a preferred term using the MedDRA dictionary. The investigator will assess AE severity and relationship to the study treatment.

A treatment emergent adverse event (TEAE) is defined as any AE with an onset date on or after date of randomization (Groups 1 and 2) or first SL BPN dose (Group 3), or any ongoing event on the date of first dose that worsens in severity after date of randomization. Only TEAEs with an onset date prior to date of last dose + 30 days will be tabulated in summary tables. For the purpose calculating treatment emergence and inclusion in summary tables, incomplete onset dates will be imputed as detailed in Appendix A.

TEAEs will be summarized by the number and percent of subjects in each primary SOC and preferred term. Subjects will be counted only once for each primary SOC and each preferred term. Summary tables of TEAEs by primary SOC, preferred term and intensity will be provided. If a subject has more than one TEAE coded to the same preferred term, the subject will be counted only once for that preferred term by using the event with the highest intensity. Similarly, if a subject has more than one TEAE within a primary SOC category, the subject will be counted only once in that SOC category by using the event with the highest intensity. TEAEs by primary SOC, preferred term and relationship to study drug will be provided as well. If a subject has more than one TEAE coded to the same preferred term, the subject will be counted only once for that preferred term by using the most related event. Similarly, if a subject has more than one TEAE within a primary SOC category by using the most related event. In addition, serious adverse events (SAE) by primary SOC and preferred term will be provided. Deaths and SAEs will be summarized similarly to AEs. All adverse event tables will also include the total number of events, counting multiple events per subject.

Injection related TEAEs, Other (non-injection related) TEAEs as well as all TEAEs will be presented by treatment group and overall. Summaries of these TEAE subsets will be presented for the following categories:

- Study drug related
- Intensity
- Relationship to injection
- Serious
- AEs which led to discontinuation
- SAEs which led to discontinuation
- TEAEs occurring in 5% or greater of any treatment group (by preferred term)

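### SAP 11.4 stops TEAE tables at post-dose day 29, so for subjects ending on monthly CAM2038, 6 of the 7 collected days after EOT are not tabulated

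*SAP*

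**What the plan says.** **SAP 11.4** limits the summary tables: "Only TEAEs with an onset date prior to date of last dose + 30 days will be tabulated in summary tables". The same section says that deaths and SAEs are handled in the same manner as AEs. It does not say whether the cut-off carries over to them.

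**Protocol 10.5.1.1** sets the collection window: "All AEs and SAEs will be collected by the Investigator from the time informed consent is signed until 7 days after the EOT visit". It expressly includes "any AEs that start after the last dose of study drug". A separate sentence requires rapid reporting of SAEs that occur "within 14 days of the EOT visit or premature discontinuation from the study".

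**The schedule.** Protocol 7.1 gives the Group 2 injections "on Day 1, Day 29, Day 57 and Day 85, for a total of 4 doses" and places EOT by the words "At the Day 113 (EOT) visit". Group 3 has its last injection on Day 92. Table 3 puts its EOT on Day 120 and its follow-up call on Day 127. The protocol synopsis and SAP 4.3 instead call Day 127 the EOT visit. Tables 1 to 3 mark the transfer to previous buprenorphine therapy at EOT (at EOT-OLE for subjects in the extension).

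**No matching limit in the protocol.** Neither the treatment-emergent definition in Protocol 10.5.1.2 nor the safety analysis in 12.3.3 has a 30-day limit.

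**The concern.** The cut-off is counted from the last dose, while collection is counted from the EOT visit. The two fit together for the weekly product, whose EOT is 7 days after the last dose. They do not fit for the monthly product, whose EOT is 28 days after the last dose, so the cut-off arrives almost as soon as the subject leaves the depot.

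The call about a week after EOT is the only scheduled safety contact once a subject has gone back to prior therapy. New events that start in that week are part of what the call is there to find, and for subjects ending on q4w most of that week is left out of the tables.

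Safety and tolerability are a secondary objective. Protocol 5.1.2 describes the earlier q4w experience as single administration, so this trial's repeat-dose q4w tables matter. The SAP gives no reason for tabulating less than the protocol collects.

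**Working it through.** **Inputs**
- Last q4w dose: Day 85 (Group 2) and Day 92 (Group 3), from Protocol 7.1.
- Last q1w dose: Day 43 (Group 1), Day 85 (Group 1 with extension) and Day 148 (Group 2 with extension), from Tables 1 and 2.
- EOT or EOT-OLE: Days 50, 92, 113, 155 and 120, from Tables 1 to 3.
- End of AE collection: "until 7 days after the EOT visit", from Protocol 10.5.1.1.

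**Step 1: reproduce the schedule.** Group 2: 85 + 28 = 113. Group 3: 92 + 28 = 120, and 120 + 7 = 127 for the call. Group 2 extension: 148 + 7 = 155, and 155 + 7 = 162 for the call. All agree with Tables 2 and 3.

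**Step 2: apply the two rules.** Last tabulated day = last dose + 30 − 1, because onset must precede day 30. Last collected AE day = EOT + 7.

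| Subjects | Last dose | EOT | Tabulated through | Collected through | Post-EOT days lost |
|---|---|---|---|---|---|
| Group 1, no extension | 43 | 50 | 72 | 57 | 0 of 7 |
| Group 1, extension | 85 | 92 | 114 | 99 | 0 of 7 |
| Group 2, extension | 148 | 155 | 177 | 162 | 0 of 7 |
| Group 2, no extension | 85 | 113 | 114 | 120 | 6 of 7 (Days 115–120) |
| Group 3, Table 3 | 92 | 120 | 121 | 127 | 6 of 7 (Days 122–127) |

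In both q4w rows the lost days are post-dose days 30 to 35 (120 − 85 = 35; 127 − 92 = 35).

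**Step 3: share of total follow-up.** Group 2: 6/120 = 5.0%. Group 3: 6/127 = 4.7%.

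**Step 4: sensitivity**
- If onset on day 30 itself counted, 5 of 7 days would be lost.
- If Group 3 EOT were Day 127, collection would run to 127 + 7 = 134. Days 122–134 would be lost: all 7 post-EOT days plus the 6 days up to and including the EOT visit. That is 13/134 = 9.7% of follow-up.
- A q4w subject who stops early loses nothing if EOT is within 22 days of the last injection (22 + 7 = 29).

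**Step 5: number affected.** About 16 in Group 3 plus at most about 16 in Group 2 gives a ceiling of about 32. Group 2 subjects who enter the extension lose nothing, and the documents do not give uptake.

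**The case against.** The strongest case for leaving the rule alone is that 30 days is a consistent on-treatment convention. SAP 8.0 uses a similar limit for concomitant medications. Protocol 9.5 says that dissociation of buprenorphine from the receptors may take "up to a month (Group 2 [for subjects not entering the open-label extension] and Group 3) following the last CAM2038 injection". The lost days lie at or beyond that month, so the limit is not arbitrary. Nothing disappears from the report either: Protocol 12.3.3 and SAP 6.0 provide listings of all safety data, and the frequencies of deaths and hospitalizations in SAP 11.4 state no cut-off. Exclusion depends on onset date, so an event first reported at the call but starting earlier stays in the tables.

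Much of this stands, and it rules out several stronger readings that a reader might infer:

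- **Depot drug still acting on days 30 to 35.** Protocol 9.5 gives an upper limit of a month for receptor dissociation. It does not show an effect in those days.
- **A downward bias of q4w against q1w incidence.** Tabulated follow-up is longer for q4w: through Day 114 or 121, against collection through Day 57 or 99 in Group 1. SAP 11.0 treats formal safety comparisons as post hoc, and Group 3 is not randomized.
- **A loss of 13 of 14 SAE days.** The 14-day sentence is a reporting duty. The same section ends AE and SAE collection at 7 days after EOT, and no contact is scheduled after the call.
- **SAEs certainly cut.** The cut-off sentence names TEAEs. The likeness between SAE and AE summaries may concern format only.

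The objection does not explain why events the protocol deliberately collects after the last dose should be missing from the tables. A convention for on-treatment events is better met by showing later events apart than by leaving them out.

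**Conclusion.** The mismatch is real and narrow. For Group 3 and for Group 2 subjects who complete the q4w interval and decline the extension, TEAEs starting on post-dose days 30 to 35 are collected but not tabulated. The same holds for the SAE tables if the cut-off carries over to them. Subjects whose last dose is q1w are not affected.

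This rests on the literal wording of the cut-off and on the Table 3 EOT day for Group 3. That EOT day is contradictory within the documents and must be reconciled; Table 3 gives the smaller loss of the two. The point is worth correcting before database lock because the data are already collected and the change costs little. It does not undermine the primary pharmacokinetic results.

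**What to change.** In SAP 11.4, replace the cut-off sentence with three rules:

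1. Tabulate TEAEs with onset through the later of last dose + 30 days and the end of protocol AE collection (EOT or EOT-OLE + 7 days).
2. Tabulate all reported SAEs and deaths regardless of this cut-off.
3. Show events with onset after transfer to prior buprenorphine therapy in a separate row or column.

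Taking the later of the two dates is essential. A window of EOT + 7 days alone would shorten tabulation for early discontinuers: with EOT at dose + 3 it would end at dose + 10, where the present rule runs through dose + 29. Under the proposed rule q4w completers are covered to max(30, 28 + 7) = day 35, q1w completers to max(30, 7 + 7) = day 30, and that early discontinuer to max(30, 10) = day 30.

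Rule 2 is needed because Protocol 10.5.1.1 asks for related SAEs with no time limit. A fixed EOT + 14 day window would drop a related SAE in Group 1 on Days 65–72 that is tabulated now (50 + 14 = 64; 43 + 29 = 72).

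Reconcile the Group 3 EOT day between Table 3, the protocol synopsis and SAP 4.3 at the same time.

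The cost is a short rewording and one extra row or column, with no new data. Some events after the transfer will enter the tables, and the separate row keeps them readable apart from on-treatment events.

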## **11.5** LABORATORY ASSESSMENTS

Chemistry, Hematology, Urinalysis and Coagulation Profile will be assessed over time (see Section 10.5.3 of the clinical study protocol for a complete list of parameters to be assessed). Summary statistics for these parameters will be presented by visit for the actual value and change from baseline for each test in each laboratory category (Hematology, Chemistry, Urinalysis, and Coagulation Profile). Shift tables will be presented for shifts from baseline lab categories to end of study laboratory category. The three laboratory categories will be: -L (below lower bound of normal range), N (within normal range), and H (above higher bound of normal range).

If a lab value is reported using a non-numeric qualifier (e.g., less than ( $\leq$ ) a certain value, or greater than (>) a certain value), the given numeric value will be used in the summary statistics, ignoring the non-numeric qualifier.

For the purpose of determining baseline, the last nonmissing observation on or prior to randomization will be used.

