# 8.2 Exclusion Criteria

Subjects will not be eligible to participate in this study if any of the following exclusion criteria are met:

- 1. Individuals meeting DSM-V substance use disorder criteria for alcohol, benzodiazepines, central nervous system (CNS) stimulants, or other drugs of abuse (excluding caffeine, tobacco or tetrahydrocannabinol [THC]/marijuana).
- Any clinically significant abnormality on the basis of medical history, vital signs, physical examination, 12-lead electrocardiogram (ECG; Fridericia's corrected QT interval [QTcF] ≥450 msec. for males or ≥470 msec. for females), and laboratory evaluations (including hematology, clinical chemistry, urinalysis at Screening), in the opinion of the Investigator.
- 3. Significant symptoms, medical conditions, or other circumstances which, in the opinion of the Investigator, would preclude compliance with the protocol, adequate cooperation in the study or obtaining informed consent, or may prevent the subject from safely participating in study, including subjects who are at a risk for gastrointestinal obstruction or paralytic ileus or who have severe respiratory insufficiency, respiratory depression, airway obstruction,

Clinical Study Protocol HS-15-549

gastrointestinal motility disorders, biliary tract disease, severe hepatic insufficiency, planned surgery and prior treatment with monoamine oxidase inhibitors.

- 4. Use (therapeutic or non-therapeutic) of opioids other than SL BPN.
- 5. Aspartate aminotransferase (AST) levels > 3 X the upper limit of normal, alanine aminotransferase (ALT), levels > 3 X the upper limit of normal, total bilirubin > 1.5 X the upper limit of normal, or creatinine > 1.5 X upper limit of normal on the Screening laboratory assessments, or other clinically significant laboratory abnormalities, which in the opinion of the Investigator may prevent the subject from safely participating in study.
- 6. Pregnant or lactating or planning to become pregnant during the study.
- 7. Diagnosis of, or currently under investigation for, fibromyalgia, complex regional pain syndrome, neurogenic claudication due to spinal stenosis, spinal cord compression, acute nerve root compression, severe or progressive lower extremity weakness or numbness.
- 8. History of chemotherapy or confirmed malignancy (except basal cell or squamous carcinoma of the skin) within the past 2 years.

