CAM2038 q4w Dose:			Dose 1 Do				ose 2 Dose 3			Dose 4									l
Day:	-21 to -1	D1	D2	D8 D15 D22	D29	D31 D36 D43 D50	D57	D59 D64 D71 D78	D85	D86	D87, D88 D89, D90 D92, D95 D99, D106	D113/ EOT	D120	D127	D134	D141	D148	D155/ EOT	D162
Informed Consent a	Х																		l
Eligibility Criteria Review b	Х	Х																	l
Medical, Psychosocial and Medication History	Х																		
Substance Use and Treatment History	Х																		1
Complete Physical Examination	Х											X						Х	
Weight, BMI	Х											X						Х	
Height	Х																		
Vital Signs C	Х	Х	Х	Х	Х	Х	Х	X	X	X	X	X	X	Х	X	Х	Х	Х	
ECG d	Х	Х		X	X	X	X	X	X	X	X	X	Х	Х	X	Х	Х	Х	1
Biochemistry, Hematology, Urinalysis, and Coagulation Profile	Х	Х			Xe		Xe		Xe			X	Х	Х	X	X	Х	X	
Pregnancy Test f	Х	Х			X		X		X			X			X			Х	
Adverse Events g	Х	Х	Х	Х	X	Х	X	Х	X	X	Х	X	Х	Х	Х	Х	Х	Х	Х
Concomitant Medications/Procedures	Х	Х	Х	Х	Х	Х	Х	Х	Х	Х	Х	Х	Х	Х	Х	Х	Х	Х	Х

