#### 12.3.3 Analysis of Safety

Exposure will be summarized by Group, treatment, and injection site, as applicable.

AEs will be coded by primary system organ class (SOC) and preferred term according to the Medical Dictionary for Regulatory Activities (MedDRA), and summarized by number and percent of subjects in each primary SOC and preferred term by Group. Summaries of these AE subsets will be presented for relationship to study drug, intensity, seriousness, AEs or SAEs leading to discontinuation. Frequencies for deaths and hospitalizations will also be summarized by Group and overall. Injection specific AEs will also be summarized.

Data for clinical laboratory tests, ECG, vital signs, and physical and injection site examinations will be summarized by Group using standard descriptive and change from baseline statistics. Shift tables and tabular summaries of abnormalities will be provided by Group, where appropriate.

The average SOWS and COWS scores over the Treatment Phase and average change from baseline (Day 1) SOWS and COWS scores will be presented.

Medications will be coded using the World Health Organization Drug dictionary and may be summarized by Group using descriptive statistics.

By-subject listings will be provided for all safety data.

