## 6.0 GENERAL CONVENTIONS

Unless otherwise stated, all statistical analyses will be performed using SAS Version 9.2 and all hypothesis tests will be conducted at a two-sided significance level of 0.05. P-values will be presented with 3 decimals and p-values that are less than 0.001 will be presented as <0.001.

Continuous (non survival related) data will be summarized using descriptive statistics: number of observations (n), mean, standard deviation (SD), median, minimum, and maximum. Frequencies and percentages will be used to summarize categorical (discrete) data. Presentations of categorical data will generally suppress percentages for items where the count is zero in order to draw attention to the nonzero counts. In general, mean, standard deviation, median, minimum, maximum, and percentages will be presented with one decimal.

Unless otherwise stated, confidence intervals, when presented, will be constructed at the two-sided 95% level. For binomial variables, the 95% confidence intervals will be constructed using the exact method.

Data listings will present all data collected on CRFs by study drug, center, and subject number. Unless otherwise stated data will be presented by treatment and overall.

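### The only categorical laboratory table in SAP 11.5, a baseline to end-of-study L/N/H shift, cannot show worsening within H, resolved abnormalities or, on one reading, the main-phase end panel of extension subjects

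*SAP*

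**What the plan says.** SAP 11.5 plans two laboratory outputs.

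- Continuous: "Summary statistics for these parameters will be presented by visit for the actual value and change from baseline for each test". SAP 6.0 defines such summaries as "number of observations (n), mean, standard deviation (SD), median, minimum, and maximum".
- Categorical: "Shift tables will be presented for shifts from baseline lab categories to end of study laboratory category". Besides L (below range), the categories are "N (within normal range), and H (above higher bound of normal range").

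SAP 11.5 has no worst-value table, no bands in multiples of ULN, no rule for unscheduled results, and no definition of end of study for subjects who enter the extension.

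Protocol 12.3.3 is wider: "Shift tables and tabular summaries of abnormalities will be provided by Group, where appropriate". SAP 11.5 carries over the first item and is silent on the second. Both documents plan listings; the SAP's wording is "Data listings will present all data collected on CRFs by study drug, center, and subject number".

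Exclusion criterion 5 (Protocol 8.2) sets the enzyme entry limit at "Aspartate aminotransferase (AST) levels > 3 X the upper limit of normal", with the same multiple for ALT and 1.5 x ULN for bilirubin and creatinine. Values between 1 x ULN and those limits do not exclude a subject under the numerical part of that criterion.

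**The concern.** Safety and tolerability is a secondary objective, and the shift table is where a reader looks to see how many subjects worsened. Three features limit what it can show.

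(a) The top category has no upper structure, so a subject already H at baseline cannot move upwards.

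(b) Only one post-baseline value per subject is used, so an abnormality that has resolved by then is not shown.

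(c) The time point is named but not defined for extension subjects. In Group 2 they switch from q4w to q1w at Day 113, so a shift read at the last visit would describe the q1w extension and not the q4w regimen that the group was set up to study.

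**Working it through.** There is no power, alpha or sample-size figure to reproduce. The check is a count of scheduled panels and a comparison of planned outputs.

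**Scheduled panels.** The source is the row "Biochemistry, Hematology, Urinalysis, and Coagulation Profile" in Protocol Tables 1 to 3, with its footnotes. Some visits carry electrolytes only (sodium, bicarbonate, potassium, magnesium, calcium). Baseline is taken as Day 1 in all groups. For Group 3 this is an assumption, because SAP 11.5 ties laboratory baseline to randomization and Group 3 is not randomized.

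| Subject | Post-baseline full panels | Electrolyte-only panels |
|---|---|---|
| Group 1, no extension | Day 50: 1 | Days 8, 15, 22, 29, 36, 43: 6 |
| Group 2, no extension | Day 113: 1 | Days 29, 57, 85: 3 |
| Group 1, extension completed | Days 50, 57, 64, 71, 78, 85, 92: 7 | 6, as above |
| Group 2, extension completed | Days 113, 120, 127, 134, 141, 148, 155: 7 | 3, as above |
| Group 3 | Day 8 (day of first CAM2038 injection), Day 120: 2 | Days 36, 64, 92: 3 |

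**Full panels outside the shift table** = full panels − 1.

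- Groups 1 and 2 without extension: 1 − 1 = 0.
- Groups 1 and 2, extension completed, end of study read as the last visit: 7 − 1 = 6, and 6/7 = 86%. The Day 50 or Day 113 panel is among the six.
- Group 3: 2 − 1 = 1 (Day 8).

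If end of study is instead read as main-phase end of treatment, an extension completer still contributes one panel of seven. It is then the Day 50 or Day 113 panel, and the six extension panels are outside. Feature (c) disappears under that reading; feature (b) does not.

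**Electrolytes.** All electrolyte-only panels precede the end-of-study value, so 6, 3 and 3 of them in Groups 1, 2 and 3 are outside the shift table under either reading.

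**Movement within H.** Take AST at 2.5 x ULN at entry (below the limit of 3) and 10 x ULN at end of study. The ratio is 10/2.5 = 4. Baseline category H, final category H: no shift. The result is the same for any rise from a baseline above ULN.

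**What the other planned outputs show of that subject.** The value can set the maximum and the maximum change in the by-visit summary, and it is in the listing. The by-visit summary is not scaled to ULN, does not tie the maximum to that subject's baseline, and does not say how many subjects passed a given level. At Day 113 it pools subjects who continue with those who stop. Protocol 10.5.3 allows extra samples when results are abnormal; with no SAP rule for them, these may reach only the listings.

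**Comparison within the SAP.** For QT and QTc, SAP 11.8 uses graded bands and counts subjects both per visit and at any visit. Laboratory tests get neither.

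**The case against.** The strongest reply is that nothing is hidden. By-visit summaries with minimum and maximum cover every scheduled panel, including Days 50 and 113. Listings cover everything and are readable with at most 24 subjects in Group 1 and about 16 in each of the others. Protocol 10.5.1.2 counts an unfavourable laboratory change as an adverse event, and Protocol 10.5.3 expects clinically significant values to be linked to medical history or an adverse event. This stands: a reader might infer that these values never appear in the report, and the documents do not support that. The limitation is confined to the shift tables and to counting subjects.

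Second, a reader might infer that the table conceals enzyme peaks during main-phase treatment. It does not. In Groups 1 and 2 enzymes are not scheduled between Day 1 and end of treatment, and in Group 3 only at Day 8, so no table could recover scheduled peaks there. Feature (b) applies to extension panels, main-phase electrolytes and unscheduled results.

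Third, a reader might infer that Group 2 results are credited to the wrong product. That goes too far. End of study is undefined, and SAP 11.0 says that safety is presented by the drug actually received, without saying how this works for a subject who switches. What stands is an ambiguity that two programmers could resolve differently.

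Fourth, SAP silence on the abnormality table does not cancel the protocol's plan, which is itself qualified by appropriateness, and no document requires ULN bands. Both are fair. Laboratory reporting is descriptive, so the case for bands rests on usefulness and on the SAP's own QTc practice.

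**Conclusion.** The point holds for the shift tables, as a minor specification gap. Followed as written, SAP 11.5 tabulates any rise from a baseline above ULN as no shift, in every group. It leaves out abnormalities that have resolved and, if end of study means the last visit, the main-phase end panel of extension subjects.

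The 6 of 7 figure applies only to subjects who complete the optional extension; identifying Day 50 or Day 113 as one of the six depends on the last-visit reading. For Group 1 and 2 subjects without extension, no full panel is lost. How many subjects will enter with raised values or take the extension cannot be known from the documents, so the number affected could be anywhere from none to most of Groups 1 and 2.

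**What to change.** In SAP 11.5:

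1. Define the shift end point as the main-phase end-of-treatment panel: Day 50 in Group 1, Day 113 in Group 2, Day 120 in Group 3 as scheduled in Protocol Table 3. Show the extension separately. SAP 4.3 and the protocol synopsis place Group 3 end of treatment at Day 127, and this must be reconciled with Table 3.
2. Add a shift from baseline to worst post-baseline value, including unscheduled results.
3. For ALT, AST, bilirubin and creatinine, replace L/N/H with bands in multiples of ULN, with cut-offs chosen by the sponsor.
4. Specify the abnormality table planned in Protocol 12.3.3, counting subjects by group.

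The cost is SAP wording and a few more tables from data already collected. Visits, sampling and study conduct do not change.
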